4. AIMS AND OBJECTIVES

Our primary hypothesis is that neurosurgical drainage, irrigation, and fibrinolytic therapy (DRIFT), which aims to lower pressure, distortion, free iron, and cytokines, will reduce severe cognitive disability in children assessed at school age.

Our secondary hypotheses are that DRIFT will improve:

- (a) cerebral visual dysfunction
- (b) sensorimotor ability
- (c) functional status
- (d) emotional/behavioural difficulties
- (e) preference based measures of health related quality of life
- (f) and reduce the health, social care and broader societal costs at age 11.

The aims of this study:

- 1) To compare cognitive function, visual function, sensorimotor ability and emotional wellbeing, between the two treatment groups in the DRIFT trial at school age.
- 2) To quantify functional status and use of community and specialist health and educational services.
- 3) To estimate the economic cost and outcomes of the DRIFT intervention by age 11, and model long-term costs and outcomes.
- 4) To quantify degree of ventricular dilatation and neurosurgical sequelae in the two treatment groups by clinical neuroimaging.

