4.2 Secondary Outcomes

- Cerebral visual function
- Sensorimotor disability
- Functional status
- Emotional/behavioural function
- Preference based measures of health related quality of life
- Costs of initial hospitalisation and treatment during the neonatal period (including emergency transportation, periods of intensive care, and readmissions based on hospital records in the UK cohort)
- Costs of subsequent health care in childhood (based on hospital records from the UK cohort)
- Health and social care costs and impact on family at age 11 (based on parent recall)

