7.4 Data Analysis

Analysis will be performed by intention to treat and hence primary outcome (cognitive score) will be assessed by comparing mean scores, and analysed using the Student t-test (unpaired). Developmental Quotient derived from age equivalent cognitive scores will be used as a continuous variable, derived from either the BAS III or BSID Bayley III scales.

For the secondary outcomes with continuous outcomes (eg Movement ABC), these will also be analysed using Students t-test, unless found in this population to not follow a normal distribution, in which case either a suitable transformations will be sought or a non-parametric approach considered.

For the binary secondary outcomes (eg functional motor impairment, Strengths and Difficulties, use of specialised health, rehabilitative or educational services) the Chi-Square or 2-tailed Fishers exact test will be used. Output from the clinical neuroimaging will be transformed into either binary (in the case of radiology reports) or continuous data (in the case of quantitative measures) and analysed as above.

Any sensitivity analyses will be performed using multivariate linear regression analysis to control for variables of interest. Co-variate variable selection will be performed a-priori for the models, and included if clinically felt to represent potentially important cofounders. To provide consistent reporting, it is anticipated that at least one sensitivity analysis will be performed: adjusting for the pre-randomisation co-variates used in the initial DRIFT trial report.

For all tests a conventional level of statistical significance at 5% will be used.

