9. ECONOMIC EVALUATION

The primary economic analysis will provide a preliminary assessment of the incremental NHS care costs of the DRIFT intervention compared to usual care based on data extracted from the hospital records combined with national and local unit cost data, discounted (at standard rates) over time. These data will be supplemented by a more detailed description of the broader impact of DRIFT on use of specialist rehabilitation services, education, informal care and family work patterns for children and their families at age 11. Due to the limited level of detail on quality of life and non-NHS resource use prior to age 11, we plan a cost consequence [18] analysis quantifying NHS resource use over the 11 year period and providing a more detailed snapshot of the broader perspective on economic (e.g. educational, rehabilitation costs, informal care, productivity) and quality of life impact at age 11. This will provide an estimate of whether the initial costs of DRIFT are counterbalanced by lower NHS secondary care costs during the first 11 years of life or lower societal costs and improved quality of life at age 11.

Modelling of long-term costs and outcomes: In secondary economic analysis, we will develop a decision tree and Markov model to estimate the cost-effectiveness (cost per quality adjusted life year [QALY]) of DRIFT compared to standard care from birth to age 18. The primary perspective will be NHS and personal social services in accordance with the NICE methods guide. However, in secondary analysis we will broaden the perspective to include education, parental expenses and lost productivity. The structure of the model will be similar to that outlined by Petrou and Khan using a Markov model to stratify cohorts of surviving children by the degree of disability (none, mild, moderate, severe) with an annual cycle length [13].

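### Section 7.4 lets skewed cost and utility outcomes fall back to a transformed or rank test, while section 9 asks about arithmetic mean cost and names no between-arm method of its own

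*Protocol*

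**What the plan says.** Section 4.2 of the protocol lists, among the secondary outcomes, preference-based quality of life and three cost outcomes: "Costs of initial hospitalisation and treatment during the neonatal period", "Costs of subsequent health care in childhood" and "Health and social care costs and impact on family at age 11". Section 4 adds a directional hypothesis, that DRIFT will improve outcomes "and reduce the health, social care and broader societal costs at age 11".

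Section 7.4 gives one rule for continuous secondary outcomes: "For the secondary outcomes with continuous outcomes (eg Movement ABC), these will also be analysed using Students t-test", unless the data prove non-normal, "in which case either a suitable transformations will be sought or a non-parametric approach considered". Its example is a motor score. Costs and utilities are neither named nor exempted.

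Section 9 sets the economic question. The primary economic analysis is a preliminary "assessment of the incremental NHS care costs of the DRIFT intervention compared to usual care". It should show whether the initial outlay is offset by lower later costs. A secondary decision model then produces incremental cost-effectiveness ratios and net monetary benefit. The only treatment of uncertainty in section 9 is the sensitivity analysis of that model. No test or interval is named for the observed difference in cost between arms.

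**The concern.** Costs in this cohort are likely to be right-skewed, because a minority of severely disabled children may use far more care than the rest. The fallback branch of section 7.4 is then open. A t-test on log costs compares geometric means. A rank test asks whether a child in one arm tends to cost more than a child in the other. Section 9 asks something else: whether money spent at the start is recovered later, which depends on totals and so on arithmetic means.

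The three comparisons agree when the arms differ only in location. They can part when the arms differ in shape, and there is reason to expect that here. DRIFT adds a procedure cost to every treated child and is hypothesised to reduce severe disability. A typical DRIFT child could cost more while the saving sits in a few children. A p-value produced under section 7.4 could then disagree with the mean incremental cost that section 9 reports from the same children.

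**Working it through.** **The plan's own figures.** The protocol states no figure for any cost comparison. Its section 5.2 figures reproduce. Odds 0.59/0.41 × 0.17 give a proportion of 0.197, and the continuity-corrected formula gives 28 per group. For 1 SD with 30 per group, power is 97%.

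**Why the targets differ.** For a lognormal cost with median m and log-SD s, the arithmetic mean is m·exp(s²/2). Assume control m = 1.0, s = 1.2 and DRIFT m = 1.6, s = 0.6.
- Control mean: exp(0.72) = 2.05.
- DRIFT mean: 1.6 × exp(0.18) = 1.92, which is 7% cheaper.
- P(DRIFT child costs more) = Φ(ln 1.6 / √(1.44 + 0.36)) = Φ(0.35) = 0.64.

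With 30 per arm (20,000 simulated trials), the rank test calls DRIFT significantly dearer in 45%, the log t-test in 48% and the raw t-test in 7%. The mean and the rank comparison point in opposite directions.

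**A total with procedure cost and later saving.** Inputs from the documents are the UK group sizes of 22 v 23 (section 5.2), severe cognitive disability of 59% v 31% at 2 years (section 3.1.2) and the planning effect of 59% v 19.7% (section 5.2). The cost distributions and the rarer-tail proportions are assumptions, because the protocol gives none.

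Model: cost = lognormal base + (if severe) lognormal extra + (if DRIFT) add-on. Setting add-on = (p_control − p_DRIFT) × mean extra makes the true mean costs equal. In the first row this is (0.59 − 0.31) × 100 = 28. The coefficient of variation is 0.5 for base and 1 for extra in rows 1–4. Rejection is at two-sided 5%:

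| Severe, control v DRIFT | Base / extra | Rank | Log t | Welch |
|---|---|---|---|---|
| 59% v 31% | 20 / 100 | 15–16% | 19–20% | 4% |
| 59% v 19.7% | 20 / 100 | 23% | 34% | 5% |
| 20% v 10% (assumed) | 50 / 200 | 36–37% | 20–21% | 5% |
| 25% v 10% (assumed) | 20 / 100 | just over 60% | about 36% | about 6% |
| 59% v 31% | 695 / 530 | 4.8–5.8% | 5.1–6.2% | 3.9–5.5% |

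In the first four rows nearly all rank and log rejections call DRIFT dearer. These figures are not bounds. With less spread (0.3 and 0.5) the first row's rank figure falls to about 9%, while the rare-tail rows rise.

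The last row uses the only cost ratio in the documents, £1,225 v £695 a year (section 3.1.2). The extra is 1,225 − 695 = 530, and 530/695 = 0.76 times base. Coefficients of variation from 0.3 to 1.0 were tried. The rejection rates are essentially nominal.

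**A cost outcome without the add-on** (later childhood or age-11 costs). With base 20, extra 100 and 59% v 31%, the rank test calls DRIFT dearer in 0.0% and cheaper in 36.0%. Welch gives 0.0% and 24.8%. In the rarer-tail settings the rank test calls DRIFT dearer in at most 0.9%. The direction is right, and at 59% v 31% the rank test is the more powerful.

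**The case against.** The strongest objection is that section 4.2 keeps the cost outcomes apart. The procedure cost falls in the neonatal outcome, and the hoped-for saving falls in the later ones. The conflicting result needs both in one variable, and that total appears only in section 9, as something to be estimated. This stands: the simulated distortion applies to the combined total and not to each listed outcome.

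Second, section 7.4 does not name costs, starts from a t-test on means, and words its fallback permissively. Economics has its own section, and the authors may have meant that section to govern. This stands in part. A reader might infer that the plan requires a rank test on costs, and it does not. But section 9 supplies no between-arm method, so section 7.4 is the only stated rule that reaches these outcomes.

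Third, a reader might infer that a rank or log test would leave the model without mean costs or utilities. The text does not support that. Section 9 draws model parameters from the trial data and not from test output, and nothing stops means being reported. Nor does section 9 state a null hypothesis of equal mean cost. Its focus on means is implied by incremental cost, cost offset and cost-effectiveness ratios.

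Fourth, an interval method is ordinary detail for an analysis plan that is not shown. That would settle the matter if the protocol were silent. It is not silent: it states a rule whose scope covers these outcomes and whose fallback changes the quantity compared, depending on the observed distribution.

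**Conclusion.** The point holds as a mismatch between the permitted test and the question asked. Section 7.4 allows a transformed or rank comparison for outcomes on which section 9 needs a difference in arithmetic means.

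The size depends on the tail and on what is added together. For a combined total with equal true means and a severe extra of 4–5 times base, the rank test calls DRIFT dearer in about 15–61% of runs, against about 3–6% for Welch. The lower end uses the 2-year proportions, and the upper end uses assumed rarer tails. At the £1,225 v £695 ratio, rejection is about nominal. That ratio is an annual figure for health and social services by age 11, so other cost periods could differ. Without the procedure add-on the effect does not arise.

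It would go too far to say that the plan's cost outcomes will in general favour the wrong arm. The primary cognitive outcome is untouched. This is a cheap improvement and not a serious flaw.

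**What to change.** In section 7.4, state that the cost outcomes and the HUI3 and EQ-5D-5L utilities are exempt from the transformation or non-parametric fallback. In section 9, state that arms are compared on these outcomes by differences in arithmetic means, in pounds or on the utility scale, with bootstrap 95% confidence intervals. Resample within arm. Medians or rank tests may be shown as description only.

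The cost is one or two sentences and a resampling of data already collected. The intervals will be wider for skewed costs, which reflects real uncertainty about the mean at this sample size. Mean-based inference is not perfect here either: across the rarer-tail settings tried, Welch's rejection rate reached about 8%. The interval should therefore carry more weight than a p-value.

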5.2 Statistical Considerations

In total 74 children (54 from Bristol and 20 from Poland) were randomised to the DRIFT trial of which 66 survived. 16 children are available for assessment in Poland and 50 in Bristol. Based on a similar effect size documented with severe cognitive disability at 2 years of age a two group continuity corrected chi-square test with a 5% two-sided significance level will have 80% power to detect the difference in severe cognitive disability between a control group proportion of 59% and odds ratio of 0.17 (i.e. an intervention proportion of 19.7%) when the sample size in each group is 28. With 60 infants (30 in each group) we will have 97% power (with an alpha of 5%) to detect a mean cognitive difference of 1 standard deviation (commonly 15 points) between the DRIFT and control groups.

45 UK children will be assessed in Bristol, and 15 Polish children in Katowice, Poland, assuming a 90% follow-up rate. It is intended to recruit 45 Children (22 DRIFT, 23 Control) from the Bristol cohort and 15 (8 DRIFT, 7 Control) from the Poland cohort.

Funding is available for the study to be completed in the UK and in Poland. **This protocol describes the UK cohort only**. The Poland cohort will be completed under a separate protocol and in accordance with local governance and regulatory requirements.

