6.3 Assessment of Motor Function and Disability

Children will be assessed by a paediatric physiotherapist:

• Full neurological assessment

- Classification of severity of cerebral palsy using the Gross Motor Classification System.
- Assessment of motor ability using the Movement ABC-2 test in mobile children. The test contains 8 tasks. The tasks cover the following 3 areas: Manual Dexterity, Ball Skills, Static and Dynamic Balance
- Head circumference, height and weight
- Clinical history (including any other identified disabilities such as hearing loss, epilepsy, feeding difficulties, subsequent neurosurgical procedures)

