6.4 Emotional and Behavioural Difficulties

The Strengths and Difficulties Questionnaire will be used. This is a brief behavioural screening tool for children and adolescents aged between 4 and 16 years of age. It comprises 25 items divided between 5 scales: emotional symptoms; conduct problems; hyperactivity/inattention; peer relationship problems; prosocial behaviour. There is a supplement which assesses impact including, chronicity, distress, social impairment and burden to others [16].

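### Section 7.4 classes the Strengths and Difficulties Questionnaire as a yes/no outcome, although it yields a score and the same section already has a route for scores

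*Protocol*

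**What the plan says.** Section 7.4 sorts the secondary outcomes into two groups.

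- **Continuous:** "For the secondary outcomes with continuous outcomes (eg Movement ABC), these will also be analysed using Students t-test". If the data are not normal, a transformation or a non-parametric method may be used instead.
- **Yes/no:** "For the binary secondary outcomes (eg functional motor impairment, Strengths and Difficulties", with service use as the third example; for these, "the Chi-Square or 2-tailed Fishers exact test will be used".

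Section 6.4 says of the SDQ: "It comprises 25 items divided between 5 scales". It adds a supplement on impact and calls the instrument a brief screening tool.

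Section 6.3 lists two motor measures that bear on the point: "Classification of severity of cerebral palsy using the Gross Motor Classification System" and "Assessment of motor ability using the Movement ABC-2 test in mobile children".

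Section 5.2 plans for 60 children, 30 per group. Section 4 names emotional/behavioural difficulties and sensorimotor ability among the secondary hypotheses.

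**The concern.** The SDQ is collected as a graded score and then assigned to a test that uses only whether a child lies above or below a threshold. This is a choice the protocol states, not a detail it leaves open. It also sits oddly with the rest of section 7.4, which keeps Movement ABC and the cognitive quotient as continuous variables.

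At stake is the precision of the comparison for one named secondary hypothesis. The follow-up draws on 66 survivors of a closed trial, so information lost in the analysis cannot be recovered by recruiting more children.

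**Working it through.** **Inputs from the protocol.** 30 children per group and a 1 SD difference for a continuous outcome (section 5.2, stated for cognition); 5% significance level (section 7.4; section 5.2 specifies two-sided).

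**Assumptions, not in the protocol.** The SDQ score is roughly normal with equal spread in both arms. The cut leaves 50%, 30% or 20% of all children, both arms together, beyond it. The true difference is 0.75 SD, with 1 SD shown alongside.

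**Step 1: the protocol's own figures.**
- Yes/no calculation: control proportion p1 = 0.59 and odds ratio 0.17 give p2 = 0.1966, so the difference is 0.3934 and the mean proportion 0.3933. Without correction, n = [1.960·√(2·0.3933·0.6067) + 0.8416·√(0.59·0.41 + 0.1966·0.8034)]² / 0.3934² = 22.98, that is 23. With continuity correction, n = (22.98/4)·[1 + √(1 + 4/(22.98·0.3934))]² = 27.8, that is 28 per group, as stated.
- Continuous calculation: the noncentrality is 1·√(30/2) = 3.873, with 58 degrees of freedom and critical value 2.002. Power is 96.8%, as stated (97%).

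The protocol gives no power for the SDQ or the motor outcomes.

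**Step 2: information kept after a split.** For a normal score with fraction c beyond the cut, relative efficiency = φ(z)² / [c(1−c)], where z is the normal quantile of the cut.

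| c | φ(z) | Efficiency | Loss | 60 children are worth |
|---|---|---|---|---|
| 0.50 | 0.3989 | 0.637 | 36% | 38 |
| 0.30 | 0.3477 | 0.576 | 42% | 35 |
| 0.20 | 0.2800 | 0.490 | 51% | 29 |

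**Step 3: power with 30 per arm.** The arms are set d/2 either side of the overall mean, and the cut k solves ½[P(Z > k−d/2) + P(Z > k+d/2)] = c. Chi-square and Fisher power come from enumerating all pairs of counts from 0 to 30. The chi-square is uncorrected: section 7.4 does not say which form is meant, and this one favours the yes/no analysis.

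| d | t-test | c | Control vs DRIFT beyond cut | Chi-square | Fisher |
|---|---|---|---|---|---|
| 0.75 | 82% | 0.50 | 64.6% vs 35.4% | 64% | 53% |
| 0.75 | 82% | 0.30 | 42.6% vs 17.4% | 57% | 47% |
| 0.75 | 82% | 0.20 | 29.9% vs 10.1% | 49% | 36% |
| 1.00 | 97% | 0.50 | 69.1% vs 30.9% | 87% | 80% |
| 1.00 | 97% | 0.30 | 46.3% vs 13.7% | 81% | 73% |
| 1.00 | 97% | 0.20 | 32.6% vs 7.4% | 72% | 60% |

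The definition of the cut matters. If the 50%, 30% and 20% referred to controls alone, chi-square power at 0.75 SD would be 60%, 49% and 41%, and Fisher 50%, 37% and 22%. With 20% of controls beyond the cut, only about 13% of all children are beyond it.

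**Step 4: why the motor grade needs a separate check.** The formula in step 2 is for a normal score. For an ordered grade with proportions p under proportional odds, the information kept by a split at cumulative proportion q is q(1−q) / [(1−Σp³)/3]. With five equally common grades the denominator is (1−5·0.008)/3 = 0.32. A cut at q = 0.4 keeps 0.24/0.32 = 75%, and a cut at q = 0.2 keeps 0.16/0.32 = 50%. Over four assumed distributions of five or six grades the loss ran from 12% to 69%. The protocol gives neither the distribution nor the threshold, so no figure can be fixed.

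**The case against.** **A screening tool is commonly read as positive or negative.** That is true, and a proportion of positives is easier to explain than a mean or rank difference. The lists in section 7.4 are examples, and nothing forbids also reporting the score. This justifies keeping the proportion as a supportive figure. It does not justify making it the only test named for the SDQ.

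**The figures rest on assumptions.** They do: normality, the cut and the effect are all assumed, and in a severely affected cohort the score may be skewed. The rank-based fallback in section 7.4 already deals with skewness. A reader might infer that the split makes the SDQ comparison likely to be inconclusive even if DRIFT works. That goes too far. At 1 SD, chi-square power is still 72% to 87% at these cuts, and at 0.5 SD the t-test itself has only 48%.

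**The missing cut-off.** The protocol states none. A threshold for a secondary questionnaire may properly be left to the statistical analysis plan, which is not at hand, so its absence is no fault here.

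**Motor severity.** A reader might infer that the gross motor grade is also to be dichotomised, with a similar loss. The protocol does not support that. Section 7.4 says only functional motor impairment and does not link it to the grade in section 6.3. It also keeps Movement ABC continuous, though section 6.3 limits that test to mobile children. Even if the link were made, step 4 shows that the size of the loss is undetermined.

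**Conclusion.** The point holds for the SDQ. Section 7.4 assigns a multi-item score to yes/no tests when a suitable route for scores stands in the same section. Under a roughly normal score the loss is 36% to 51% of the information for cuts with 50% to 20% of children beyond them. At an assumed 0.75 SD, power falls from about 82% to between 49% and 64% with chi-square, or 36% and 53% with Fisher. At 1 SD it falls from 97% to between 72% and 87%, or 60% and 80%.

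For functional motor impairment the point is conditional. If that outcome is derived from the gross motor grade, a rank or ordinal analysis would keep more information, by an amount the documents do not establish.

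The matter concerns secondary outcomes only. The primary analysis is untouched, and both figures in section 5.2 reproduce.

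**What to change.** In section 7.4, take Strengths and Difficulties out of the yes/no list. Analyse the SDQ total difficulties score and the impact score by the existing route for continuous outcomes, with its rank-based fallback if they are skewed. Report the proportion above a published cut-off, stated in advance, as supportive.

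State which measure functional motor impairment comes from. If it is the gross motor grade, use a rank or ordinal method, and place children without cerebral palsy in a defined lowest category, since the grade describes the severity of cerebral palsy. A proportional-odds model would add an assumption that a rank test avoids.

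The cost is a sentence or two and no new data. The small downside is that a mean or rank difference is less directly interpretable than a proportion of screen-positive children, which the supportive figure largely makes good.

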After initial feasibility testing showed DRIFT was technically possible and promising, the DRIFT randomised trial started recruiting in 2003. Eligible babies were preterm, had an IVH and expanded the cerebral ventricles over pre-determined limits. With parental consent, 74 babies were randomised in Bristol and Katowice, Poland to either DRIFT or to standard therapy which consisted of non-surgical conventional management (lumbar punctures to control excessive expansion and pressure symptoms). If repeated lumbar punctures were needed, a ventricular reservoir was inserted to facilitate tapping CSF.

Short term outcomes in the DRIFT trial showed no difference in shunt surgery or death. There was a significant increase in secondary bleeding in the DRIFT group. Magnetic resonance (MR) imaging was carried out on clinical indications in 36 of the 50 Bristol survivors.

At 2 years post term, severe disability or death was significantly reduced in the DRIFT group, when neurodevelopment was assessed by "blinded" observers [2]. There was an important decrease in severe cognitive disability (Bayley mental development index 3 SDs below mean) from 59% to 31% (adjusted odds ratio: 0.17 [95% CI 0.05-0.57]) and the difference in median MDI was more than 18 points. Developmental quotient at 2 years correlated significantly with qualitative grading of MR brain images at term. Sensorimotor disability remained substantial at 2 years: overall, 48% were unable to walk, and 20% were unable to communicate. Ventricular enlargement is typically greatest in the occipital areas and 9% of the children had no useful vision. Severe sensorimotor disability was less common in the DRIFT group but without reaching statistical significance.

However, while (relatively) short term neurodevelopmental measures are essential in the initial management of perinatal interventions, longer term measures provide far greater validity in assessing long term functioning (and the medical, societal and financial implications of these).

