6.1 Cognitive Assessments

Assessment will be undertaken by child psychologists.

Cognitive testing in this group of children needs to use a method with a wide spread of abilities as some of the study children have very significant disabilities (Cognitive score below 55). The British Ability Scales (BAS III) comprise 21 short tests, each measuring particular types of knowledge, thinking and/or skills (Elliott and Smith. GL Assessment; London. 2012). The final type of score is "age equivalent". This is the age at which the score achieved by the child was average. The BAS III has a basal threshold at a developmental age of 3 years. In the event that children do not attain the basal scoring threshold of the BAS III, the cognitive and language scales from the Bayley Scales of Infant and Toddler Development III (BSID III) (Bayley N. Harcourt Assessment: San Antonio; 2006) will be administered. This test also yields Developmental Age Equivalent score from 1 month to 3 years. In order to compare scores in all children, developmental age scores will be converted into a developmental quotient score: [developmental age equivalent score \div biological age at assessment x 100] for each child. This allows severely delayed children to have a cognitive score rather than being labelled as "untestable".[14] The final cognitive score for children of all abilities will therefore be a cognitive developmental quotient and a continuous variable.

The BAS_III and BSID III will be adapted for use in Polish speaking children.

The individual scales for BASIII are:

- Block building
- Copying
- Early number concepts
- Matching letter-like forms
- Matrices
- Naming Vocabulary
- Number Skills
- Pattern Construction
- Picture Construction
- Picture Similarities
- Quantitative Reasoning
- Recall of Designs
- Recall of Digits Backwards
- Recall of objects

- Recognition of pictures
- Speed of information processing
- Spelling
- Verbal Comprehension
- Verbal Similarities
- Word definitions
- Word reading

The individual scales for BSID III are:

- Cognitive Scale
- Language Scale (receptive and expressive language)

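### The primary t-test ignores baseline covariates and adjustment is left to a sensitivity analysis, although the 2-year effect that this follow-up extends and is powered on was covariate-adjusted

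*Protocol*

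**What the plan says.** Section 7.4 fixes the primary analysis: "primary outcome (cognitive score) will be assessed by comparing mean scores, and analysed using the Student t-test (unpaired"). The outcome is DQ, treated as continuous.

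Adjustment has a lower status. "Any sensitivity analyses will be performed using multivariate linear regression analysis to control for variables of interest". Covariates are to be chosen in advance on clinical grounds. So that reporting is consistent, it is anticipated that "at least one sensitivity analysis will be performed: adjusting for the pre-randomisation co-variates used in the initial DRIFT trial report". The protocol does not list those covariates.

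Section 3.1.2 gives the 2-year result for severe cognitive disability as a fall "from 59% to 31% (adjusted odds ratio: 0.17 [95% CI 0.05-0.57"]). Section 5.2 takes the adjusted figure as its planning effect, "a control group proportion of 59% and odds ratio of 0.17 (i.e. an intervention proportion of 19.7"%), and states that "a two group continuity corrected chi-square test with a 5% two-sided significance level will have 80% power" "when the sample size in each group is 28".

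The planned 60 are 45 UK children (22 DRIFT, 23 control) and 15 Polish children (8 DRIFT, 7 control). The Polish cohort runs under a separate protocol. Section 6.1 adds: "The BAS_III and BSID III will be adapted for use in Polish speaking children".

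**The concern.** The trial's own 2-year headline was an adjusted effect, and the follow-up borrows that effect for its sample size. The school-age headline, however, will come from a test that uses no baseline information, and the analysis that matches the 2-year report is only a secondary check.

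Section 5.2 counts 74 children randomised and 66 survivors, so numbers cannot be raised. Adjustment for prognostic baseline variables is one of the few remaining ways to gain precision. If the arms differ by chance on such a variable, the unadjusted estimate carries that difference. If crude and adjusted results then diverge, the plan has already committed to the less precise one as primary.

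**Working it through.** **1. The plan's own figures.** Control 59% and odds ratio 0.17 give intervention odds 0.17 × 0.59/0.41 = 0.245, a proportion of 0.245/1.245 = 19.7%. The continuity-corrected formula at two-sided 5% then gives 28 per group, with 80.3% power. For the continuous score, 30 per group and 1 SD give 97.2% by the normal approximation and 96.8% by the noncentral t. Both stated figures reproduce.

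**2. Crude against adjusted at 2 years.** The crude odds ratio is not printed. From the percentages it is (0.31/0.69)/(0.59/0.41) = 0.449/1.439 = 0.31, or 0.30 to 0.33 allowing for rounding. The adjusted value is 0.17.

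**3. What the gap can show.** The odds ratio is non-collapsible, so a conditional and a marginal value differ even when the arms are perfectly balanced. Suppose a normal prognostic score, balanced between arms, has SD 1.5 to 2 on the logit scale. With control risk 59% and conditional odds ratio 0.17, the marginal odds ratio is then 0.28 to 0.34, which covers 0.31. The gap therefore fits covariates that are prognostic, imbalanced, or both.

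**4. Gain for the DQ comparison.** *Assumptions:* covariates explain R² = 0.2 to 0.4 of DQ variance, and SD is 15, 20 or 25. Section 5.2 calls 15 points a common SD but gives no SD for these children. Adjustment multiplies the residual SD by √(1 − R²), so the standardised difference becomes d/√(1 − R²). Power is from the noncentral t with noncentrality d√(n/2), n = 30, with 58 df unadjusted and 54 adjusted (four covariate terms assumed). The true difference is 15 points.

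| SD | d | Unadjusted | R² = 0.2 | R² = 0.3 | R² = 0.4 |
|---|---|---|---|---|---|
| 15 | 1.00 | 96.8% | 98.9% | 99.5% | 99.8% |
| 20 | 0.75 | 81.5% | 89.1% | 92.6% | 95.8% |
| 25 | 0.60 | 62.8% | 72.3% | 77.9% | 83.8% |

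In terms of sample size, 1/(1 − R²) is 1.25 to 1.67, so 60 children carry the information of about 75 to 100. At SD 15, the difference detectable with 80% power falls from 11.0 points to 9.9, 9.2 and 8.6 at R² = 0.2, 0.3 and 0.4. Losing a fifth degree of freedom changes power by less than 0.1 percentage point.

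**5. Country.** The Polish share is 8/30 = 26.7% in the DRIFT arm and 7/30 = 23.3% in the control arm. A 15-point mean difference between countries, taken for illustration, would move the pooled arm difference by 15 × 0.033 = 0.5 points. Confounding by country is negligible as planned. A country term would mainly remove between-country variance.

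**6. Adjusting the binary endpoint.** I simulated 3,000 trials of 60 children per setting, with 59% vs 31%, conditional odds ratio 0.17, and covariates explaining the whole crude-to-adjusted gap (logit SD 1.75). Adjusted logistic power was 76–79%, against about 50% for the corrected and 60% for the uncorrected chi-square. With no treatment effect and 45% risk, the adjusted likelihood-ratio test rejected in 5.8% of trials with one covariate, 7.2% with four and 7.6% with six. The power figure is a best case, and the ordinary logistic test is anti-conservative at this size.

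**The case against.** The strongest reply is that an unpaired t-test in a randomised comparison is unbiased and holds its error rate, and that section 7.4 already plans the adjusted analysis, with covariates fixed in advance. Only the order of the two analyses is in dispute. On the protocol's planning value of 1 SD = 15 points, the gain is 2 to 3 percentage points of power. All of this stands, and it limits how strongly the point can be put. The remaining argument is that the order matters when the cohort is closed, the true SD is unknown and the adjusted model is already planned.

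Several stronger readings are tempting but not supported:

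- *The move from 0.31 to 0.17 shows that the unadjusted result is biased.* It may be wholly non-collapsibility, 0.31 lies inside the adjusted interval of 0.05 to 0.57, and a mean DQ difference is not subject to non-collapsibility.
- *The result cannot be compared with the 2-year report.* The planned sensitivity analysis exists for that comparison.
- *Pooling the two countries without a country term confounds the result.* The arms are planned nearly equal within country, and Poland has its own protocol. Whether centre is already among the 2-year covariates cannot be seen.
- *Linear regression is the wrong adjusted model.* It is right for DQ. That sections 2 and 4.1 name a binary endpoint while section 7.4 tests a mean is a separate problem. So is the use of an adjusted odds ratio in an unadjusted sample-size formula.

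Nor can this be deferred to an unseen SAP: section 7.4 itself states the unadjusted test as primary.

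**Conclusion.** The point holds as an inexpensive improvement to a valid analysis. The plan gives its headline to the less precise of two analyses it already intends to run, and the one it relegates matches the adjusted effect it extends and is powered on.

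The benefit is small if DQ has an SD near 15 and material if the SD is 20 to 25, where it is roughly 8 to 21 percentage points of power for a 15-point difference. These figures rest on assumed SD and R² values. The 2-year odds ratios suggest prognostic and/or imbalanced covariates but do not fix an R² for DQ at school age. That the covariates can be retrieved is inferred from their use in the earlier report and from section 7.1, where the trial database is used to trace participants.

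**What to change.** In section 7.4, make the primary analysis a linear regression of DQ on arm plus the pre-randomisation covariates of the 2-year report, listed by name before outcome data are examined. If the UK and Polish cohorts are pooled and centre is not already on that list, add country. Keep the unadjusted t-test as a supportive analysis.

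If an adjusted analysis of severe cognitive disability is reported, use logistic rather than linear regression, with few covariates and a small-sample method such as Firth penalisation, as supportive only.

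The cost is a change of wording, a few degrees of freedom, and confirmation that the baseline covariates can be retrieved for every child assessed.
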